#### 6.11.1.1 Progressive Multifocal Leukoencephalopathy (PML)

A patient with multiple sclerosis developed progressive multifocal leukoencephalopathy (PML) after nearly 8 months of treatment with another SIP1 agonist, and enablement of the John Cunningham (JC) virus is therefore a potential adverse effect of this therapeutic class.

Patients in this trial should therefore be monitored for any new onset or worsening of neurological signs and symptoms. Signs and symptoms associated with PML are diverse, progress over days to weeks, and include progressive weakness on one side of the body or clumsiness of limbs, disturbance of vision, and changes in thinking, memory, and orientation leading to confusion and personality changes. The progression of deficits usually leads to death or severe disability over weeks or months. If PML is suspected, withhold dosing and refer to a neurologist; if confirmed, discontinue dosing permanently.

The investigator or subinvestigator will administer the subjective PML checklist during screening to exclude patients with positive responses from enrolling into the study. The subjective PML checklist will be administered at each site visit (except Day -1) to probe for symptoms suggestive of PML. Any patients reporting signs and/or symptoms of PML will undergo objective testing and may be referred to a neurologist for a full evaluation.

A copy of the PML checklist is provided in [Appendix 1](#).

### 6.11.2 Serious Adverse Events and Expedited Reporting of Adverse Events

A Serious Adverse Event (SAE) is any untoward medical occurrence that at any dose results in the following outcomes:

- Death
- Is Life-Threatening
- Required/Prolonged Hospitalization
- Disability/Incapacity
- Congenital Anomaly/Birth Defect
- Important Medical Event

SAEs will be captured from the time of ICF signature to 30 days after the last dose of study drug, and will be monitored until resolution or stabilization.

An important medical event that may not result in death, be life-threatening, or require hospitalization may be considered a SAE when, based upon appropriate medical judgment, it may jeopardize the patient and may require medical or surgical intervention to prevent one of the outcomes listed in this definition. Examples of such a medical event includes allergic bronchospasm requiring intensive treatment in an emergency room or at home, blood dyscrasias, or convulsions that do not result in in-patient hospitalization, or the development of drug dependency or drug abuse.

Elective hospitalization and/or surgery for clearly pre-existing conditions (for example a surgery that has been scheduled prior to the patient's entry into the study) will not be reported as a SAE. All other hospitalizations, including elective hospitalizations for any condition that was not pre-existing, will be reported as a SAE.

Any AE considered serious by the investigator or which meets SAE criteria must be reported to PPD Pharmacovigilance (PVG) using the remote data capture (RDC) system within 24 hours from the time study site personnel first learn about the event.

The following contact information is to be used for SAE reporting:

## **PPD Medical Affairs/Pharmacovigilance**

**PPD PVG Hotline:** [REDACTED]

**PPD PVG Fax line:** [REDACTED]

In the event that RDC entry is not possible (e.g., system failure or access problems), the study site should complete the paper SAE report form and fax the form to PPD PVG within 24 hours of awareness of the event. The RDC system should be updated as soon as it is available.

A full description of every SAE will need to be provided to PPD PVG (this may be supported by source documentation such as laboratory reports or a discharge summary should the patient be hospitalized).

Other safety issues as defined in ICH Topic E2A, 21 code of federal regulations (CFR) §312.32, and EU Volume 10 also qualify for expedited reporting. In these situations the process will be as detailed for SAEs above:

- SAEs which could be associated with the trial procedures;
- SAEs and AEs of special interest that could materially influence the benefit-risk assessment of a medicinal product, such as: a clinically important increase in the rate of a serious suspected adverse reaction over that listed in the investigator brochure.

### **6.11.2.1 Patient and Patient-partner Pregnancy**

Patients who become pregnant during the study will be discontinued immediately. Although not considered an SAE or AE, pregnancies occurring during the period of study drug administration (Day 1 to Week 12) until 30 days after the last dose of study drug should be reported to the sponsor contact and IRB/IEC in the same manner as an SAE.

Pregnancies will be followed every trimester through the first well baby visit. For female partners whom become pregnant by male study patients during the course of the study, reasonable efforts will be made to collect information on the partner's pregnancy through the first well baby visit as provided by the male study patient.

### **6.11.3 Assessment of Adverse Event Severity**

The severity of each AE will be assessed at onset by a nurse and/or physician. When recording the outcome of the AE the maximum severity of the AE experienced will also be recorded. The severity of the AE will be graded according to the CTCAE v4.03 definitions, listed below:

**Grade 1:** Mild; asymptomatic or mild symptoms; clinical or diagnostic observations only; intervention not indicated.

**Grade 2:** Moderate; minimal, local or noninvasive intervention indicated; limiting age-appropriate instrumental Activities of Daily Living (ADL)\*.

**Grade 3:** Severe or medically significant but not immediately life-threatening; hospitalization or prolongation of hospitalization indicated; disabling; limiting self-care ADL\*\*.

**Grade 4:** Life-threatening consequences; urgent intervention indicated.

**Grade 5:** Death related to AE.

**Activities of Daily Living (ADL):**

\*Instrumental ADL refer to preparing meals, shopping for groceries or clothes, using the telephone, managing money, etc.

\*\*Self-care ADL refer to bathing, dressing and undressing, feeding self, using the toilet, taking medications, and not bedridden.

#### 6.11.4 Assessment of Adverse Event Relationship to Study Medication

The relationship of an AE to investigational product(s) will be classified using modified WHO criteria (Edwards and Biriell, World Health Organization Collaborating Centre for International Drug Monitoring 1994) as follows.

**Related:** a clinical event, including laboratory test abnormality, with a reasonable time sequence to administration of the drug, unlikely to be attributed to concurrent disease or other drugs or chemicals, and which follows a clinically reasonable response on withdrawal (dechallenge). Rechallenge information is not required to fulfill this definition; or an event that could also be explained by concurrent disease or other drugs or chemicals where information on drug withdrawal may be lacking or unclear.

**Not related:** a clinical event, including laboratory test abnormality, with sufficient evidence to accept that there is no causal relationship to drug administration (e.g., no temporal relationship to drug administration, because the drug was administered after onset of event; investigation shows that the drug was not administered; proof of other cause; etc.); or an event with a temporal relationship to drug administration which makes a causal relationship improbable, and in which other drugs, chemicals or underlying disease provide plausible explanations.

#### 6.11.5 Assessment of Adverse Event Outcome

Outcome of AEs will be defined according to ICH Topic E2B, ICH Guideline.

- Recovered/Resolved
- Recovered/Resolved with Sequelae

- Recovering/Resolving
- Not Recovered/Not Resolved
- Fatal
- Unknown

#### 6.11.6 Action Taken for Adverse Event

Action taken for AEs will be documented according to the following:

- Concomitant medication or other treatment
- Withdrawal from the study

#### 6.11.7 Action Taken for Study Drug

Any action taken with study drug will be defined according to ICH Topic E2B, ICH

[figure not shown]
Guideline and documented in the CRF according to the following:

- Drug Withdrawn
- None (not changed)
- Dose Interrupted
- Unknown
- Not Applicable

#### 6.11.8 Follow-up of Adverse Events Present at Last Scheduled Study Visit

Adverse events present at the last study day (Week 12) that require follow-up or a repeat laboratory test will be followed-up according to the site's standard practice for AE follow-up.

## 6.13 Removal of Patients from the Trial or Study Drug

Patients experiencing a significant infection as judged by the investigator will be discontinued from the study drug.

The study may be terminated early if, in the opinion of the sponsor, investigator, or IRB/IEC, an unacceptable risk to the safety and welfare of patients is posed by the continuation of the study in light of review of the key safety data.

Patients will be free to withdraw from the study at any time should they so wish. A patient may be withdrawn from the study for any of the following reasons (including but not limited to):

- Clinical investigator may remove a patient if, in his/her opinion, it is in the best interest of the patient
- Withdrawal of consent - Any patient may withdraw his/her consent from the study at any time. The investigator should make a reasonable attempt to document the specific reason why consent was withdrawn.
- Deviation/noncompliance with the protocol or study drug
- An adverse event
- Lost to follow up

[figure not shown]
### 6.13.1 Handling of Withdrawals

[figure not shown]
Although a patient is not obliged to give his/her reason for withdrawing prematurely, the investigator will make a reasonable effort to obtain the reason while fully respecting the patient's rights. If there is a medical reason for withdrawal, the patient will remain under the supervision of the study physician until in satisfactory health. Reasonable efforts will be made to contact a patient who fails to attend any follow-up appointments, in order to ensure that he/she is in satisfactory health.

[figure not shown]
If a patient is prematurely discontinued from this study, every attempt will be made to follow the Week 12 procedures.

[figure not shown]
### 6.13.2 Replacements

[figure not shown]
Patients who terminate early from the study will not be replaced.

## **8 DATA MANAGEMENT**

### **8.1 Data Collection**

All data (ECGs, clinical laboratory data, and all other study-related data) will be collected according to the sponsor / CRO's SOPs or according to study site standard if applicable.

### **8.2 Data Coding**

#### **8.2.1 Adverse Events**

Adverse events will be coded using the most current Medical Dictionary for Regulatory Activities (MedDRA) and tabulated, including categorical information of interest such as onset and resolution times, time of onset relative to dose, severity at onset, maximum severity, causal relationship to study medication, and action taken. Whenever possible, a constellation of signs and symptoms should be recorded as a unifying diagnosis (e.g., self-limited fever, runny nose, cough, and scratchy throat should be captured as an upper respiratory infection rather than by the individual signs and symptoms). AEs will be regarded as 'pre-treatment' if they occur between screening and the time of administration of the first dose of etrasimod. All other AEs that occur after the first dose of study medication will be considered to be 'treatment-emergent'.

#### **8.2.2 Concomitant Medications and Non-drug Treatments**

Due to the variability in how medications are recorded, a standard naming convention is required in order to tabulate this data effectively. A common method of standardization is to categorize medications by their Preferred Term. In order to do this, medications will be coded using the World Health Organization Drug Dictionary (WHO DD), Format C.

#### **8.2.3 Medical History**

Medical history will be coded using the most current MedDRA-version.

## **9 PLANNED STATISTICAL METHODS**

Details of the statistical analyses will be included in a separate statistical analysis plan (SAP) which will be finalized before database lock. If, after database lock, changes are made to the pre-specified statistical analysis plan, the changes will be listed along with an explanation as to why they occurred in the Clinical Study Report.

### **9.1 Hypotheses and Objectives**

#### **9.1.1 Objectives**

##### **9.1.1.1 Efficacy Objectives**

The objectives will be to determine the effect of etrasimod in Inflammatory Bowel Disease patients on the clinical improvement of active skin extra-intestinal manifestations.

##### **9.1.1.2 Safety Objective**

The safety objective will be to determine the safety profile and tolerability of etrasimod

#### **9.1.2 Hypotheses**

There are no formal hypothesis tests specified in this open-label study due to the lack of control treatment group.

### **9.2 Sample Size and Power Calculations**

There is no formal sample size estimation for this proof-of-concept open-label study. Sample size of 10 - 20 subjects is reasonable to assess proof-of-concept of the efficacy of etrasimod in the target population.

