## SYNOPSIS

Name of Drug:	Etrasimod (APD334)
Indication	Inflammatory Bowel Disease (IBD) with active skin extra-intestinal manifestations (EIM) including Psoriasis, Erythema Nodosum (EN), and Pyoderma Gangrenosum (PG)
Sponsor:	Arena Pharmaceuticals, Inc. [name]
Name of Sponsor Contact	██████████ MD CMO Research and Development Arena Pharmaceuticals, Inc. [name] Phone: ██████████ email: ██████████
Name of Principal Investigator(s):	Multi-center
Medical Monitor:	██████████, MD Medical Monitor Arena Arena Pharmaceuticals, Inc. [name] Phone: ██████████ email: ██████████
Test Product, Dose and Mode of Administration:	
 
• ██████████ etrasimod once daily (q.d.) for 12 weeks
 
• Patients should be instructed to take their tablet on an empty stomach (after overnight fast) and to avoid eating for 1 hour after dosing. Patients should be advised not to crush, break, chew, or dissolve the tablet and to take study medication with an adequate amount of water.
 

Concurrent Control:	None. This is an open-label study.
Objectives:	The efficacy objective is to determine the treatment effect of etrasimod in Inflammatory Bowel Disease patients on the clinical improvement of active skin extra-intestinal manifestations. The safety objective is to determine the safety profile and tolerability of etrasimod.
Study Design	This is a phase 2a, proof-of-concept, multicenter, open-label, single-arm study in 10-20 IBD patients with active skin extra-intestinal manifestations. All visits in the study are ambulatory visits. The screening period

will last up to 4 weeks and is followed by a 12-week treatment period. During this treatment period patients will take one tablet of study medication once per day. The last dose is planned to be taken one day before the last treatment visit at week 12. A follow-up visit will take place 2 weeks after the end of treatment.

Study Site(s)	This study will be conducted in approximately 3 clinical centers.

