Patient Population:	
Inclusion Criteria
 

1. Men or women of age 18 to 80 years, inclusive.

2. Able to give signed informed consent and willing and able to comply with the study requirements.

3. Considered to be in stable health in the opinion of the investigator as determined by:

a.) A pre-study physical examination with no clinically significant abnormalities unrelated to IBD.

b.) Vital signs (VS) at screening: pulse rate <math>\geq</math> 55 bpm, systolic blood pressure (SBP) <math>\geq</math> 90, and diastolic blood pressure (DBP) <math>\geq</math> 55 mmHg.

c.) Liver function tests (ALT/AST, bilirubin and alkaline phosphatase) <math><</math> 2x the upper limit of normal [ULN].

d.) All other pre-study clinical laboratory findings within normal range, or if outside of the normal range are not deemed clinically significant in the opinion of the investigator.

e.) 12-lead electrocardiogram (ECG) showing no clinically significant abnormalities in the opinion of the investigator (for confirmation please refer to exclusion criteria # 22).

f.) A chest x- ray showing no evidence of active pulmonary disease (a chest x-ray taken within the previous 12 months from the screening visit may also be used).

g.) Ophthalmology evaluation (by an ophthalmologist) without evidence of macular edema, supported with OCT where available (dependent on site capability) no later than 3 months prior to screening.

4. Patients receiving stable treatment for IBD and EIM as defined in section 6.12.

5. Diagnosis of active psoriasis, erythema nodosum or pyoderma gangrenosum by Investigator assessments.

6. Diagnosis of ulcerative colitis (UC) or Crohn's disease (CD) established prior to screening by clinical and endoscopic evidence.

7. Eligible female patients must be:

a.) non-pregnant, evidenced by a negative serum human chorionic gonadotropin (hCG) pregnancy test at screening and a urine dipstick pregnancy test at Day 1.

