--	---

	
may interfere with compliance with the study procedures.
 
33. History of any clinically significant medical condition that, in the investigator's opinion, would preclude participation in the study.
 
34. Use of moderate to strong inhibitors of CYP2C9.
 
35. History of severe renal or hepatic impairment.
 
36. Inability to attend all the study visits or comply with study procedures.
 
37. Prior exposure of etrasimod.

Duration per Patient:	Up to 18 weeks total: up to 4 weeks for screening, followed by a 12-week treatment period and a follow-up visit 2 weeks after the end of treatment.
Sample Size:	Up to 20 patients (with up to 10 patients with anti TNF-alpha induced psoriasis).
Efficacy Endpoints:	
As this is a proof-of-concept study, all endpoints are exploratory.
 
 
- UC endpoint: Change from baseline in stool frequency, rectal bleeding, PGA (Physicians Global Assessments) at weeks 1, 2, 4, 8 and 12.
 
- CD endpoint: Change from baseline in disease activity score at week 1, 2, 4, 8 and 12.
 
- Change from baseline in endoscopic improvement/histologic healing using endoscopy or flexible proctosigmoidoscopy. (Only if there are signs of inflammation at screening another evaluation will be performed at week 12).
 
- Change from baseline in level of fecal calprotectin at week 4, 8 and 12.
 
- Change from baseline in Physician Global Assessments for active skin extra-intestinal manifestations (PG, EN and psoriasis) at week 1, 2, 4, 8 and 12.
 
- Change from baseline in Patients Global Assessments for active skin extra-intestinal manifestations (PG, EN and psoriasis) at week 1, 2, 4, 8 and 12.
 
- Change from baseline in the Dermatology Life Quality Index (DLQI) score at week 1, 2, 4, 8 and 12.
 
- Psoriasis endpoint only (all other endpoints are for all skin manifestations): Change from baseline in Psoriasis
 

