### **3 INVESTIGATIONAL PLAN**

#### **3.1 Overall Study Design and Plan**

APD334-006 is an open-label, phase 2, proof-of-concept single-arm study designed to evaluate the efficacy and safety of etrasimod in IBD patients with active skin extra-intestinal manifestations.

[figure not shown]
Up to 20 IBD patients with acute psoriasis, pyoderma gangrenosum or erythema nodosum (with up to 10 patients with anti TNF-alpha induced psoriasis) will be included in the study.

[figure not shown]
Patients will receive once daily (q.d.) [REDACTED] doses of etrasimod for 12 weeks.

[figure not shown]

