### **9.6.2 Subgroup Analyses**

Efficacy endpoints will be analyzed on following patient populations. Certain subgroups may be combined when deemed clinically necessary.

- PG EIM
- EN EIM
- psoriasis EIM
- psoriasis due to anti TNF-alpha treatment

Other subgroup analyses based on demographics (such as sex, age, race, etc.) may be performed when deemed appropriate-

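### Does a cap of 10 anti-TNF-induced psoriasis cases, with no floor for other patients, leave the stated 10–20 target patients undelivered?

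*Combined protocol and SAP*

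**What the plan says.** The protocol states the study size in five places and in two forms.

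- **A range.** The Synopsis (Study Design) describes a "single-arm study in 10-20 IBD patients with active skin extra-intestinal manifestations". Section 9.2 first says "There is no formal sample size estimation for this proof-of-concept open-label study" and then "Sample size of 10 - 20 subjects is reasonable to assess proof-of-concept of the efficacy of etrasimod in the target population". The Synopsis (Statistical Analyses) repeats the range.
- **Ceilings only.** The Synopsis (Sample Size) gives "Up to 20 patients (with up to 10 patients with anti TNF-alpha induced psoriasis", and Section 3.1 gives "Up to 20 IBD patients with acute psoriasis, pyoderma gangrenosum or erythema nodosum (with up to 10 patients with anti TNF-alpha induced psoriasis".

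No current text sets a minimum number of patients without anti-TNF-induced psoriasis, a minimum per skin condition, or an order of entry. Inclusion criterion 5 asks for "Diagnosis of active psoriasis, erythema nodosum or pyoderma gangrenosum by Investigator assessments" and says nothing about the cause of the psoriasis. Section 9.3 takes into the efficacy analysis every enrolled patient with a baseline and at least one later measurement. Section 9.6.2 then names four groups for efficacy analysis. Psoriasis as an EIM is one, and "psoriasis due to anti TNF-alpha treatment" is another.

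**The concern.** Section 9.2 calls 10 to 20 patients enough for proof of concept in a target population that it does not define. The operative enrolment rule limits anti-TNF-induced psoriasis by an absolute number, not by a share. At the lower end of the range, all 10 patients could have a drug-induced reaction. The efficacy objective concerns skin EIM, Section 9.6.2 lists the drug-induced group apart from psoriasis as an EIM, and Section 1.1.1 calls it paradoxical.

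Read that way, a trial run exactly as written could reach its stated size with nobody who answers its main question. The study has no control arm, and the Synopsis intends to set its confidence intervals beside historical data. An estimate from an unknown mix would be hard to place there.

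**Working it through.** **1. Is there a figure to reproduce?** No. Section 9.2 disclaims a formal calculation, Section 9.1.2 specifies no hypothesis test, and no effect size, alpha, power or precision is stated. The check is therefore a count, followed by a reading of the text.

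**2. The count.** Inputs (Synopsis Sample Size, Section 3.1): total N at most 20; anti-TNF-induced cases at most 10. Guaranteed other patients = N − min(10, N) = max(0, N − 10).

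| N | Guaranteed others | Largest anti-TNF share |
|---|---|---|
| 10 | 0 | 10/10 = 100% |
| 15 | 5 | 10/15 = 67% |
| 20 | 10 | 10/20 = 50% |

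Zero other patients needs total enrolment of 10 or fewer and every patient of one type.

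**3. How likely is the extreme?** The documents do not give the share q of entrants with anti-TNF-induced psoriasis, so q is assumed. With independent entry and N = 10, P(no others) = q^10:

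- q = 0.50: 0.001
- q = 0.75: 0.056
- q = 0.90: 0.35

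Section 1.1.1 allows a rough illustration. It gives paradoxical psoriasis in 1.6–8.8% of anti-TNF users and psoriasis in 7–11% of IBD patients. Take the combination that most favours the concern: everyone on anti-TNF, 8.8% against 7%, and no EN or PG. Then q = 8.8/(8.8 + 7) = 0.557 and q^10 ≈ 0.003. The case mix at the sites is unknown, so this shows only the order of size.

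**4. Is anti-TNF-induced psoriasis outside the target population?** The count matters only if it is.

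- *For inclusion:* the Indication row lists psoriasis among the skin EIMs without regard to cause. Criterion 5 and Section 4.1 do the same. Section 3.1 counts the anti-TNF cases within the 20. Section 1.1.1 ends its argument on S1P4 and interferon-alpha by proposing a role for drugs like etrasimod in paradoxical psoriasis.
- *For exclusion:* Section 9.6.2 lists the group separately. A subgroup list divides the enrolled population; it removes nobody from it.

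The weight of the text is for inclusion. On that reading every total from 10 to 20 meets Section 9.2.

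**5. Precision, if only the other patients counted.** Section 9.6.1 names no interval method; exact (Clopper-Pearson) limits are assumed. At about 50% response: 10/20 gives 27–73%, 5/10 gives 19–81%, and 2/5 gives 5–85%. The skin endpoints listed in the Synopsis are changes from baseline, so the half-width for a mean change is closer to use. In SD units it is t/√n: 2.093/√20 = 0.47 at n = 20 and 2.262/√10 = 0.72 at n = 10. The loss is real, but the plan claims no precision that it would breach.

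**6. Would a different rule gain anything?**

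- Requiring at least 10 others among 20 restates the current ceilings: 20 − 10 = 10.
- Capping anti-TNF cases at half guarantees 5 others at N = 10, 8 at N = 15 (at most 7 anti-TNF) and 10 at N = 20. It still does not secure 10 at the lower sizes. As a running rule it can also hold back eligible patients until someone else enrols.
- Reporting the anti-TNF group separately is already in Section 9.6.2.

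**The case for a change.** The best case for acting is that the protocol leaves the population behind its estimate open. Section 9.2 never defines its target population, and Section 9.6.2 lets subgroups be combined on clinical judgement with no rule fixed beforehand. Withdrawals are not replaced (Section 6.13.2) and Section 9.3 requires a post-baseline value, so the evaluable numbers can fall below the guaranteed ones. The extreme of no other patients is remote, but partial dilution at totals of 11 to 19 is not. A subgroup table cannot supply patients whom the enrolment rule did not secure.

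Much of this is true as description. The size wording does conflict, the term is undefined, and 10 patients without anti-TNF-induced psoriasis are guaranteed only if enrolment reaches 20. It does not amount to a defect. The mix will be known exactly at the end, patients can be classified by group, and the plan commits to analysing each group. Every endpoint is labelled exploratory and nothing is tested, so the choice of headline population protects no error rate. A floor would be a reasonable alternative design. Its cost is slower entry to a study of at most 20 patients at about three centres, and leaving it out is a fair trade-off.

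**Conclusion.** The arithmetic is right and the conclusion drawn from it is not. The rule guarantees max(0, N − 10) patients without anti-TNF-induced psoriasis, but the stated size is undelivered only if those cases lie outside the target population. The indication, the entry criteria, the enrolment rule and the rationale all point the other way.

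The two forms of the size are a clerical inconsistency. The Protocol Amendment Summary records the move to the ceiling wording in the Synopsis Sample Size row and Section 3.1, and the other three places keep the range. The two forms share the same maximum of 20, and no analysis depends on the lower figure. Analysts can fill the undefined term sensibly by describing the overall result as that of all enrolled patients, stating the anti-TNF share, and showing that group on its own as Section 9.6.2 provides.

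This rests on the current text admitting psoriasis of any cause and on the group summaries being produced. The probabilities assume independent entry and a share that the documents do not give. If anti-TNF cases made up about 90% of entrants and enrolment stopped at 10, the extreme would no longer be remote (0.35), but it would be visible in the report. No change to the plan is called for.
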